7.1 Immunotherapy with Pembrolizumab

Protocol therapy will consist of 1 cycle administered every 21 days. Treatment will continue until disease progression and no longer benefiting clinically, or unacceptable adverse event. Treatment may continue beyond disease progression per iRECIST guidelines. That is, treatment may continue beyond assessment of progressive disease (PD) provided the patient is clinically stable and felt to be continuing to benefit from therapy. A patient may be deemed clinically stable provided that no worsening of performance status has occurred, there have been no clinically relevant increases in disease-related symptoms such as pain or dyspnea that are thought to be associated with disease progression, and there has been no requirement for intensified management of disease-related symptoms, including increased analgesia, radiotherapy, or other palliative care. Repeat imaging should be obtained within 4-8 weeks if feasible, and no later than 3 months. If the subsequent scan shows additional new lesions or increase in new lesion size (sum of measurements \geq 5 mm), treatment should be discontinued.

Arm	Agent	Dose	Route	Day	Rx
A	Pembrolizumab	200 mg	IV*	Day 1	Every 3 weeks
B	Pembrolizumab + RT	200 mg + RT**	IV*	Day 1	Every 3 weeks***

* Infused over approximately 30 minutes (range: 25-40 minutes).

** Patients will receive 3 fractions of radiation to a total dose of 24 Gy (8 Gy x 3 fractions).

Administration of radiotherapy will occur to a single site for subjects randomized to the pembrolizumab and radiotherapy group.

***Radiotherapy can be initiated after the first dose of immunotherapy and must be completed before 12 weeks after first dose of immunotherapy administered.

7.2 Radiotherapy

Administration of radiotherapy will occur to a single site for subjects randomized to the pembrolizumab and radiotherapy group.

Radiotherapy can be initiated after the first dose of immunotherapy and must be completed before 12 weeks after first dose of immunotherapy administered.

There is no size criterion for irradiated site and should follow this priority list:

1. Growing area that may cause symptoms.
2. Area that can tolerate the highest dose prescription (8 Gy x 3) based on normal tissue constraints.
3. If all above equal, then order would be Pelvis, Abdomen, Liver, Lung, Bone.

The goal of RT treatment is to deliver appropriate radiotherapy while minimizing exposure of surrounding normal tissues. Many different ways of delivering RT exist, and all are acceptable as long as the treating institution has completed the necessary credentialing. Most commercially available electron and photon-producing treatment units are allowed. As such, conventional linear accelerators and specialized linear accelerators with image guidance (e.g., Novalis, Trilogy, Synergy, Artiste, TrueBeam, Unity, ViewRay) are allowed. These units can be used with conformal dose delivery or IMRT. Specialized dose painting accelerators (e.g., Cyberknife, or Tomotherapy) are allowed provided they meet the technical specifications of the protocol and are used in a fashion that passes the

credentialing required by the protocol. Conventional linear accelerators without add-on IGRT must have some other IGRT capability like CT-on-rails in the treatment room.

IGRT is required for this study. Either 3DCRT or IMRT (including VMAT) are acceptable planning techniques. IMRT (including VMAT) can result in dosimetric inaccuracies in circumstances where tumor motion is not properly considered. Planning techniques may differ for each lesion to be treated provided that the tumor motion is properly accounted for with each technique when the target or targets are in or near the thorax region.

i. Dose Fractionation

Patients will receive 3 fractions of radiation to a total dose of 24 Gy.

For each metastatic location, Variation Acceptable range is described for plan scoring. Doses falling outside the range of Per Protocol and Variation Acceptable will be scored as Deviation Unacceptable.

There should be a minimum of 40 hours between treatments to any single metastasis.

ii. Technical Factors

Physical Factors

Only photon (x-ray) beams with photon energies \geq 6MV or electron beam with electron energies 4 MeV – 20 MeV will be allowed. For metastases located within 3 cm of the lungs, photon energies of 6-10MV are required. Cobalt-60 and charged particle beams (including proton and heavier ions) are not allowed.

For lung central and lung peripheral metastases, photon beam energies $>$ 10 MV are allowed only for a limited number (\leq 50% of all beams or all beam angles) of beams that must travel more than a cumulative distance of 10 cm through soft tissue (not lung) to reach the isocenter OR a shorter distance if the tumor abuts the chest or abdominal wall (i.e., to spare skin dose).

FFF photon beams are allowed if the institution has performed SBRT credentialing with FFF beams.

Treatment Technology

This protocol requires photon or electron treatment. Techniques including 3DCRT, IMRT, VMAT are allowed. Delivery on LINACs, Tomotherapy, or CyberKnife are acceptable.

Minimum Field Aperture (Field Size) Dimension

Because of uncertainties in beam commissioning resulting from electronic disequilibrium within small beam apertures, an equivalent square field dimension of 3 cm is required for any field used for treatment delivery for sites using standard 3-D conformal technique where nearly all of the PTV is encompassed for each beam. It is understood that this may exceed the technical requirements for small lesions. In such cases, the prescription dose is still prescribed to the edge of the defined planning treatment volume (PTV). For sites using dose painting including IMRT techniques, whereby design the entire PTV is not encompassed for each beam, smaller beam apertures are allowed. In addition, if the site has specifically commissioned the beams for smaller field sizes, and if these same beams have been employed in IROC Houston QA Center credentialing, they may reduce the minimum field aperture requirement to the size that has been commissioned and credentialed.

All institutions must use heterogeneity correction dose calculation algorithms approved by the IROC Houston QA Center independent of the treatment planning technique.

Stereotactic Targeting

For the purposes of this protocol, the term ‘stereotactic’ implies the targeting, planning, and directing of radiation beams along any trajectory in 3-D space toward a target of known 3-D coordinates. The coordinate system is defined by reliable ‘fiducials.’ A fiducial may be external or internal to the patient’s body. External fiducials may relate to a frame or treatment device. Internal fiducials may be implanted markers OR reliably identifiable anatomy that is clearly visible on orthogonal kV imaging, including the tumor itself. In all cases, the relationship between the fiducial and the actual tumor position in real-time should be reliably understood for both planning and treatment.

Isocenter Placement

When using a gantry mounted linear accelerator for this protocol, the isocenter is defined as the common intersection point of gantry, collimator, and couch rotation for the treatment unit. For other types of treatment units (e.g., Tomotherapy or CyberKnife), a reference point in space that is typically positioned at the center of the target is used instead of a mechanical isocenter.

iii. Localization, Simulation, and ImmobilizationPatient Positioning (Immobilization)

Patients will be positioned in a stable pose conducive to allowing accurate reproducibility of the target position throughout treatment. Positions uncomfortable for the patient should be avoided so as to prevent uncontrolled movement during treatments. Patient immobilization must be reliable enough to ensure that the gross tumor volume (GTV) does not deviate beyond the confines of the planning treatment volume (PTV).

Positioning patients directly on the couch and relying solely on image-guidance for reproducible set-up is strongly discouraged.

Simulation

All patients will undergo CT-based treatment planning in custom made immobilization devices. CT scan range must allow simultaneous view of the patient anatomy and fiducial system for stereotactic targeting (if used), and be adequate to ensure contouring of all targeted metastases, as well as necessary organs at risk (OAR), defined below. High-resolution CT scans should be obtained with uniform slice thickness of $\leq 3\text{mm}$ throughout. If a single CT scan cannot be obtained due to a large spatial separation between metastases (i.e., cervical and femoral metastases), or planning system slice number limitation, multiple CT scans are allowed provided that OAR are entirely encompassed in a single CT scan.

Use of Contrast Agents

The use of IV contrast will be required for liver metastases unless using an MRLinac. For other metastases (central & peripheral lung, cervical/mediastinal, abdominal-pelvic, and spinal/paraspinal), the use of IV contrast is encouraged but will be left to the discretion of the treating physician.

The use of other contrast agents is left to the discretion of the treating oncologist. Vascular contrast from the planning dataset is recommended to be converted to water equivalent density if used for planning. Duplicate planning datasets obtained prior to injection of intravenous contrast may be used for dose calculation.

Respiratory Motion Assessment and Management

All metastases with potential for respiratory motion should be evaluated by appropriate means including 4D CT scan, implanted fiducial marker, or fluoroscopy at the time of simulation.

Respiratory motion management (RMM) including abdominal compression, active breathing control, breath hold, end expiratory gating, or fiducial marker tracking, is recommended for any metastasis to be treated with motion $> 5\text{mm}$. A recommended approach would be to use an ITV technique for motion $< 1\text{cm}$, but for motion $> 1\text{cm}$ (typically too large for a free breathing ITV) motion management including but not limited to abdominal compression, active-breathing control (ABC), gating, breath hold, etc. should be used.

Localization Using Daily IGRT

As an RT protocol, this study requires the use of IGRT. IGRT is a computer assisted process that uses imaging devices that generate a series of coordinates for shifting the patient support system in three orthogonal directions (sometimes also including rotational changes) to position the treatment beams relative to target regions. The allowed technologies are as follows: cone-beam CT (CBCT) using either a specially mounted kV imaging head or the MV treatment beam with an opposed electronic imaging panel, dual fixed-position in-room kV imaging systems that are orthogonal or near orthogonal, an in-room standard diagnostic CT scanner that is geometrically linked to the treatment unit, and the Tomotherapy or MRLinac approach. Although all of these units are allowed, some might not be appropriate for some disease sites. For example, orthogonal imaging techniques result in overlapping structures that are not as easily visualized compared to 3D cone-beam approaches. Simple portal imaging approaches that do not use computer assistance are not considered suitable for this study.

When the treatment equipment does not include any device that allows direct visualization of anatomical structures using the treatment beam, the recommendations of AAPM Task Group Report 142 for testing the coincidence of the imaging and treatment reference points must be implemented. When specialized units such as Tomotherapy or Cyberknife are employed, the relevant AAPM guidance documents should be followed for testing the coincidence of imaging and treatment systems.

IGRT Requirements

The minimum IGRT requirement for each metastatic location is listed in Table 5-3. Volumetric imaging refers to 3D modalities (e.g., kV cone-beam, MV cone-beam, CT onrails, MRLinac), while orthogonal imaging refers to 2D modalities (e.g., kV OBI, ExacTrac). For volumetric imaging, appropriate CT window/level thresholds must be employed for registration at each metastatic location as outlined in Table 5-4. Additional IGRT may be employed at the discretion of the treating physician (i.e., orthogonal kV imaging prior to required volumetric imaging or volumetric imaging even if only orthogonal kV imaging is required). Note that when orthogonal kV imaging is employed for sites where respiratory motion is expected and not controlled via motion management techniques, care must be taken to ensure accurate targeting of the ITV within the treatment. For example, static kV imaging at an undetermined breath hold position would not be adequate IGRT for treating a free-breathing lung tumor.

Metastatic Location	Minimum IGRT Requirement	
	No Fiducials	With Fiducials**
Lung--Peripheral ⁺	Volumetric (3D)	Orthogonal kV (2D)
Lung—Central ⁺	Volumetric (3D)	Orthogonal kV (2D)
Mediastinal/Cervical LN	Volumetric (3D)	N/A
Liver ⁺	Volumetric (3D)	Orthogonal kV (2D)
Spinal	Orthogonal kV (2D)	Orthogonal kV (2D)
Osseous*	Orthogonal kV (2D)	N/A
Abdominal-pelvic ⁺	Volumetric (3D)	Orthogonal kV (2D)

*NOTE: When osseous/rib metastases are classified into another metastatic location, follow the IGRT guidelines for that site.

**NOTE: When a metastasis contains an implanted fiducial that is clearly visible on kV orthogonal or volumetric imaging, either method can be used.

+NOTE: Registration to a soft tissue surrogate for the tumor is recommended for lung, liver, and abdominal-pelvic metastases for both 3D and 2D IGRT datasets.

Use of a shortened CT planning scan for registration may be important for IGRT systems that cannot handle a large number of CT slices. A subset of the planning CT scan can be uploaded to the IGRT system for localization of each metastasis. The CT data should include the metastasis of interest plus at least 5 cm superiorly and inferiorly.

iv. Target Volumes

Site Location Definition:

Site to be treated will be assigned to one of the seven “Metastasis Locations” as described below.

Site Locations:

Lung Central: GTV within 2 cm of proximal bronchial tree as described in RTOG 0813/0915:

Tumor within or touching the zone of the proximal bronchial tree, defined as a volume 2 cm in all directions around the proximal bronchial tree (carina, right and left main bronchi, right and left upper lobe bronchi, intermedius bronchus, right middle lobe bronchus, lingular bronchus right and left lower lobe bronchi) [See Figure 5-1]. Tumors that are immediately adjacent to mediastinal or pericardial pleura (PTV touching the pleura) also are considered central tumors and are eligible for this protocol. A visual representation is shown below in Figure 5-1.

[figure not shown]

Figure 5-1

Lung Peripheral: Metastases within the lung parenchyma with GTV outside of the proximal bronchial tree as described above.

Mediastinal/Cervical LN: Mediastinal: GTV arising within the anatomic space between the lungs, above the diaphragm, and below the thoracic inlet at the level of the top of the sternal notch. Cervical Lymph nodes: GTV occurring within cervical lymph node Levels I-VI and/or retropharyngeal spaces.

[figure not shown]
- Sternal metastases will be assigned to the mediastinal/cervical lymph node location based on potential for normal tissue toxicity.

Liver: GTV arising within the liver.

- Rib metastases immediately adjacent to the liver will be assigned to the liver metastasis location based on potential for normal tissue toxicity.

Spinal: Metastases will be assigned to the spinal/paraspinal site if the GTV arises within the vertebral bodies expanded by 1 cm. Spinal metastases, shown in Figure 5-2 in black, can involve:

- (a) The vertebral body only **OR**
- (b) The vertebral body and pedicle **OR**
- (c) Posterior elements only

Figure 5-2**Figure 2: Diagram of Spine Metastasis and Target Volume**

For each of these metastases, the PTV delineation will include:

- (a) the involved vertebral body and both pedicles (solid red line in Figure 5-2a) **OR**
- (b) a more generous delineation of the involved vertebral body and both pedicles (dashed red line in Figure 5-2b) **OR**
- (c) the involved vertebral body, both pedicles, and the anterior and posterior elements of the spine (solid red line in Figure 5-2b) **OR**
- (d) the spinous process and laminae (solid red line in Figure 5-2c)
 - The target volume may be chosen at the discretion of the treating Radiation Oncologist based on the extent of tumor involvement.
 - Spinal metastases with epidural extension will only be included if there is > 3 mm gap between the edge of the epidural metastasis and edge of the spinal cord.
 - Metastases arising in the ribs within 1 cm of the edge of the vertebral body should be included in the spinal metastasis location, but osseous metastases planning guidelines are to be used.

Osseous: GTV arising within an osseous structure, part of the axial skeleton, not included in the spinal definition.

- Rib metastases that are within 1 cm of the vertebral bodies will be classified into the spinal metastasis location given the similar normal tissues at risk.
- Rib/scapular metastases within the thorax adjacent to lung parenchyma will be classified into the lung metastasis location given the similar normal tissues at risk.
- Rib/osseous metastases adjacent (≤ 1 cm) to mediastinal or cervical structures will be classified into the mediastinal/cervical lymph node location given the similar normal tissues at risk.
- Rib metastases adjacent (≤ 1 cm) to the liver will be classified into the liver location given the similar normal tissues at risk.
- Rib metastases adjacent to the stomach/abdominal wall will be classified into the intra-abdominal location given the similar normal tissues at risk.
- Sternal metastases will be considered part of the

mediastinal/cervical lymph nodes location given the similar normal tissues at risk.

Abdominal-pelvic: GTV arising within the anatomic space defined by the diaphragm superiorly, the genitourinary diaphragm inferiorly including the peritoneal and retroperitoneal spaces, not including liver, osseous, or spinal metastases.

Target Volume Definition Based on Metastatic Location:

Specific RT planning parameters depend on the location of the treated metastasis as well as mechanism used for motion management/evaluation. The table below defines appropriate planning CT window/leveling, recommended additional modality scans to be fused, as well as how to define the GTC, ITV, CTV, and PTV for each metastatic location. Only rigid registration will be permitted for multi-modality fusion. In general, the GTV is defined as the entirety of the metastasis as seen on planning CT scan aided by additional diagnostic imaging studies (i.e., PET/CT or MRI). Use of additional diagnostic studies is left to the discretion of the treating physician. The CTV=GTV; there is no margin added for microscopic extension. In general, either a helical CT or 4DCT will be used for defining the GTV/ITV depending upon the tumor motion encountered, although both scans may be acquired at the time of simulation. Typically, the ITV is generated using either expiratory/inspiratory phase scans or from reconstructed maximum intensity projection (MIP) scans. Maximum/minimum intensity projections (MIP/MinIP) should be used with caution because the MIP reconstruction for lung or MinIP reconstruction for liver may erroneously define an ITV in cases of significant irregular breathing or when tumors abut soft tissue structures (e.g., the diaphragm for MIP) or fat (for the MinIP).

Metastatic Location							
Planning Parameter	Lung Central	Lung Peripheral	Liver	Abdominal -pelvic	Mediastinal /Cervical Lymph Nodes	Osseos	Spinal
CT window/level	Pulmonary/ Mediastinal	Pulmonary/ Mediastinal	Hepatic	Soft tissue	Pulmonary / Mediastinal	Bone/ soft tissue	Bone/ soft tissue
Additional Studies	PET/CT	PET/CT	PET/CT MRI	PET/CT MRI	PET/CT	PET/CT MRI	PET/CT MRI
Multiphase CT	N/A	N/A	N/A	Yes	N/A	N/A	N/A
Anatomy of focus for multi-modality fusion	Bony Anatomy	Bony Anatomy	Liver	Bony Anatomy	Bony Anatomy	Bony Anatomy	Bony Anatomy
GTV definition	Metastasis	Metastasis	Metastasis	Metastasis	Metastasis	Metastasis	Metastasis
CTV definition	= GTV/ITV* = GTV/ITV*	= GTV/ITV* = GTV/ITV*	= GTV/ITV* = GTV/ITV*	= GTV/ITV* = GTV/ITV*	= GTV/ITV* = GTV/ITV* ⁺	= GTV = GTV	= GTV = GTV
PTV axial expansion	= CTV + 5mm** = CTV + 5mm**	= CTV + 5mm** = CTV + 5mm**	= PTV in RTOG 0631** (see Figure 5-2)				

PTV craniocaudal expansion	= CTV + 7mm**	= PTV in RTOG 0631** (see Figure 5-2)					
---	------------------	------------------	------------------	------------------	------------------	------------------	---

***NOTE:** A GTV to ITV expansion of greater than 1cm in any one direction is strongly discouraged and alternative respiratory management technique is suggested.

****NOTE:** When osseous/rib metastases are classified into other specific metastatic locations, the planning guidelines for that metastatic location should be used. If rib metastases are grouped into the spinal metastasis location, then the metastasis should be contoured as defined for osseous metastases, but the prescription doses for the spinal region should be used.

+NOTE: Mediastinal lymph nodes should undergo motion assessment and an ITV should be generated to account for motion.

v. Treatment Planning

Planning Techniques

General Considerations: A variety of planning techniques can be used to deliver RT. General guidelines include the following:

- Multiple coplanar or non-coplanar beam arrangements are acceptable.
- Typically 7-13 static radiation beams with equal weighting are used. It is recommended that at least 10 beams be used when possible.
- A minimum field dimension of 3 cm should be observed while treating small metastases with 3D-CRT.
- Dynamic conformal arcs are acceptable. It is recommended that arcs span a total for all beams of 340 degrees.
- For non-IMRT or dose painting techniques, the conformal field aperture size and shape should correspond nearly identically to the projection of the PTV along a beam's eye view (i.e., no additional "margin" for dose buildup at the edges of the blocks or MLC jaws beyond the PTV). The only exception will be when observing the minimum field dimension of 3 cm when treating small lesions.
- The prescription isodose line covering 95% the PTV will generally be 80-90%, but may range from 60-90% where the maximum dose is 100%. As a result, a "hotspot" will exist within the PTV that is equal to the prescription dose divided by the prescription isodose line (i.e., $45\text{ Gy}/0.6 = 75\text{ Gy}$ when 45 Gy is prescribed to the 60% isodose).
- Doses higher than the prescription isodose (i.e., hotspots) should be manipulated to occur within the target.

Dose calculations: All dose distributions shall include corrections for tissue heterogeneities. The approved algorithms to be used are found on the IROC Houston website (<http://irochouston.mdanderson.org>).

Successful treatment planning will require accomplishment of all of the following criteria:

1. Normalization: The treatment plan should be initially normalized such that 100% corresponds to the maximum dose within the PTV (MAXPTV). While this point will typically correspond to the PTV center of mass, it can be located elsewhere within the PTV.
2. Prescription Isodose Surface Coverage: The prescription isodose surface will be chosen such that 95% of the target volume (PTV) is

conformally covered by the prescription isodose surface. Doses less than 95% of the prescription dose are restricted to the outside edges of the PTV as shown in Figure 5-3. The prescription isodose surface selected MUST be $\geq 60\%$ and $\leq 90\%$ of the dose maximum within the PTV (MAXPTV). The MAXPTV corresponds to the normalization point (100%) of the plan as noted in number 1 above.

[figure not shown]
3. **Target Dose Heterogeneity**: Rather than prioritizing target dose homogeneity, RT treatment planning prioritizes adequate minimum target coverage and rapid dose fall-off gradients outside of the target. Hot spots within targets are generally accepted without consequence since targets are mostly tumor. The only exception is when the hotspot within the PTV also intersects an OAR (see Figure 5-3).
4. **Critical Organ Doses**: Respect all critical organ dose-volume limits.
5. **High-Dose Spillage**:
 - a. **Location**: Any dose $> 105\%$ of the prescription dose should occur within the PTV and not within the normal tissues outside the PTV. See Figure 5-3.
 - b. **Volume**: Acceptable isodose distributions should be as conformal as possible. To this end, the ratio of prescription isodose volume to PTV should be as small as possible.
 - i. The ratio of the prescription isodose volume to the PTV volume should be < 1.2 . Acceptable variations include a ratio of 1.2-1.5. Ratios above 1.5 will be considered unacceptable deviations. The prescription line for each lesion will be contoured for calculation of this ratio. The prescription line will be labelled as V_5000 with the 5000 changing to reflect the prescription dose in cGy. Contours with identical doses should be distinguished.
 - ii. Guidelines for the ratio of the 50% prescription isodose volume to the PTV volume (R50%) and for the maximum dose at 2cm (D2cm) from the PTV are given in Table 5-5. Additionally, the 50% isodose volume may be elongated deliberately in order to avoid OAR, thereby making it difficult to meet the guidelines in Table 5-5. This is acceptable as long as normal tissue constraints are met.
 - iii. Given that conformal tumor coverage is often more difficult to achieve in lung than in more homogeneous organs, these ratios should serve as a guide for liver, abdominal-pelvic, mediastinal/cervical metastases as well.
 - iv. Elliptically shaped metastases as well as extremity metastases may not meet these guidelines. This is acceptable as long as normal tissue constraints are respected. These criteria will not be required in treating very small tumors (< 2.5 cm axial GTV dimension or < 1.5 cm craniocaudal GTV dimension) in which the required minimum field size of 3 cm results in the inability to meet a conformity ratio of 1.5.

Table 5-5

PTV Volume (cc)	Ratio of 50% Prescription Isodose Volume to PTV Volume, R50%	Maximum Dose at 2cm (D2cm) from PTV in any direction as % of Prescribed Dose
1.8	< 7.5	<57.0
3.8	< 6.5	<57.0
7.4	< 6.0	<58.0
13.2	< 5.8	<58.0
22.0	< 5.5	<63.0
34.0	< 5.3	<68.0
50.0	< 5.0	<77.0
70.0	< 4.8	<86.0
95.0	< 4.4	<89.0
126.0	< 4.0	<91.0
163.0	< 3.7	<94.0

NOTE: For values of PTV dimension or volume not specified, linear interpolation between table entries is required.

NOTE: For tumors within 2 cm of the skin, it may be difficult to meet the values for D2cm and R50%. In these cases, these criteria will not be used.

Figure 5-3

1. Prescription dose 50 Gy
2. Prescription isodose 80%
3. 105% of prescription dose

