3.2.1 Documentation of disease

- Histologically confirmed metastatic urothelial carcinoma

3.2.2 Patients must be either ineligible for platinum treatment or platinum refractory as defined below:

Platinum-ineligible: If patients meet any one of the following criteria:

1. Impaired renal function [creatinine clearance (CrCl) of <30 mL/min]
2. Grade >2 peripheral neuropathy
3. NYHA Heart Failure of >3

Platinum-refractory: If patients meet any one of the following criteria:

1. Prior platinum-based perioperative chemotherapy within 12 months of relapse
2. Prior platinum-based chemotherapy for metastatic disease

3.2.3 Measurable disease as defined in Section 11.0.

Patients must have at least one measurable site ≥ 1 cm in diameter per RECIST 1.1 and a site targetable for radiotherapy. Measurable site must not overlap with radiated site such that measurable site cannot receive >2 Gy per fraction.

Patients must have measurable disease, defined as at least one lesion that can be accurately measured in at least one dimension (longest diameter to be recorded for non-nodal lesions and short axis for nodal lesions). See Section 11.0 for the evaluation of measurable disease.

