13.4 Sample Size Calculation

The sample size was determined with nQuery (v8.6.1.0) under the following assumptions:

- 1) one-sided alpha = 0.10
- 2) power = 90%
- 3) arm A (control arm) tumor response rate = 20%
- 4) minimum detectable increase in response rate = 20% (absolute)
- 5) one interim analysis for futility after 50% of patients followed for response

This requires a total sample size = 136 evaluable patients (68 in each arm). The sample size will be inflated by 5% to account for ineligible or non-evaluable patients, so the target accrual is 144 patients.

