13.6 Primary Analysis Plan

Interim analysis for futility: There will be one interim analyses for futility. The interim analysis will occur after 50% of the patients (i.e. 68) have been followed for six months. If at this time the tumor response for Arm A (immunotherapy alone) is greater than the tumor response rate for Arm B (immunotherapy plus radiation), which would correspond to an OR > 1, the recommendation will be to stop the trial due to futility.

Final Analysis: The final analysis will occur after 136 evaluable patients have completed 6 months of follow-up. The tumor response rate will be analyzed with a Mantel-Haenszel test (that accounts for the randomization stratification factors) comparing the response rates between the two treatment arms. The analysis will be a modified intent-to-treat analysis where patients are ineligible or not evaluable will be excluded. An additional analysis will be conducted using logistic regression analysis that includes treatment arm and any baseline variables that are imbalanced between the arms as explanatory variable.

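### A targetable radiotherapy site is an eligibility criterion left undefined until Arm B planning, so site-related ineligibility is more likely to be found, and dropped from the primary analysis, in Arm B

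*Combined protocol and SAP*

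**What the plan says.** **Entry.** Section 3.2.3 asks for at least one measurable lesion "and a site targetable for radiotherapy". It adds that the measurable site must not overlap the radiated site, in terms of dose per fraction. Section 3.2.7 bars prior radiotherapy to either site. Section 4.4 has staff verify eligibility before enrollment. Section 3 does not say what 'targetable' means, does not refer to Section 7.2, and does not require the intended site to be recorded.

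**Planning.** Section 7.2 applies to patients randomized to pembrolizumab plus radiotherapy. It gives a priority list for choosing the site. Under Target Volumes it says "Site to be treated will be assigned to one of the seven" listed locations, with an epidural-gap condition for spinal lesions. Organ dose limits follow in Table 5-7. For bone, the location is defined as "GTV arising within an osseous structure, part of the axial skeleton, not included in the spinal definition".

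**Analysis.** Section 12.5 calls a registered patient ineligible if any eligibility criterion is not met, and requires no further follow-up of ineligible patients who continue protocol treatment. Section 13.6 says: "The analysis will be a modified intent-to-treat analysis where patients are ineligible or not evaluable will be excluded". Neither section says when, on what information, or by whom ineligibility is judged. The trial is open-label (13.1), and response is assessed by the treating physician (13.2.1).

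**The concern.** Two entry conditions, a targetable site and no overlap with the radiated site, can be fully tested only once a radiotherapy plan exists. Plans exist only in Arm B, after randomization. If planning shows that a patient did not meet a criterion, Sections 12.5 and 13.6 allow that patient to leave the primary analysis. The same patient in Arm A would never be planned and would normally stay in.

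Dropping randomized patients on information gathered mainly in one arm means that the analysed arms are no longer the randomized ones. If the dropped patients differ in prognosis from the rest, the response-rate comparison is biased even when radiotherapy has no effect. It may not be recoverable later: an ineligible patient who continues treatment needs no further follow-up under Section 12.5, so an analysis of all randomized patients could lack that patient's response.

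**Working it through.** **Inputs from the plan.** Section 13.4: "one-sided alpha = 0.10", power 90%, "arm A (control arm) tumor response rate = 20"%, "minimum detectable increase in response rate = 20% (absolute"), 136 evaluable patients, 144 accrued after a 5% allowance. Section 4.6.2: 1:1 allocation, so 144/2 = 72 per arm.

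**Step 1: the plan's own figure.** With pooled variance and no continuity correction,

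n per arm = [1.2816 × √(2 × 0.30 × 0.70) + 1.2816 × √(0.20 × 0.80 + 0.40 × 0.60)]² / 0.20² = 67.3, rounded up to 68, or 136 in total.

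Then 136/0.95 = 143.2, rounded up to 144. Both figures reproduce; the sample size is not in question. This is a fixed-sample formula, and the futility look is not modelled.

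**Step 2: analysed Arm B rate with no treatment effect.** Let k of 72 Arm B patients be dropped and none in Arm A. Let the true response be 20% in both randomized arms, and let q be the rate at which the dropped patients would have responded. The analysed Arm B rate is (72 × 0.20 − kq)/(72 − k). For k = 4 and q = 0, this is 14.4/68 = 21.2%.

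**Step 3: type I error.** Exact enumeration of two binomials (72 against 72 − k), rejecting when the pooled z-statistic is at least 1.2816. With no exclusions the error is 0.101.

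| q among dropped | k = 4: Arm B rate | k = 4: type I error | k = 8: Arm B rate | k = 8: type I error |
|---|---|---|---|---|
| 0% | 21.2% | 0.132 | 22.5% | 0.173 |
| 10% | 20.6% | 0.115 | 21.25% | 0.131 |
| 20% | 20.0% | 0.099 | 20.0% | 0.096 |
| 30% | 19.4% | 0.085 | 18.75% | 0.068 |

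The 20% row carries no bias; its small departures from 0.10 come from the discreteness of the test.

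**Step 4: scale of the assumed counts.** The documents give no rate of planning failure. The 5% allowance is trial-wide (0.05 × 144 = 7.2 patients), covers all causes and is not split by arm. Four patients are 4/144 = 2.8% of accrual. Eight are 5.6%, slightly more than the whole allowance, so k = 8 is an upper illustration.

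**Step 5: price of keeping such patients.** Suppose all 144 are analysed as randomized, unirradiated Arm B patients respond at 20%, and the other Arm B patients respond at 40%.

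- k = 4: Arm B rate (68 × 0.40 + 4 × 0.20)/72 = 38.9%, exact power 89%.
- k = 8: Arm B rate (64 × 0.40 + 8 × 0.20)/72 = 37.8%, exact power 87%.
- k = 0: 72 per arm at 20% against 40%, exact power 92%.

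Steps 3 and 5 use an unstratified test in place of the planned Mantel-Haenszel test.

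**The case against.** The strongest reply is that no section says a planning failure makes a patient ineligible. The criteria are in Section 3.2, apply to both arms and are checked before enrollment. Most of Section 7.2 is method: the location list assigns image guidance, margins and contour names, and the organ limits mostly grade plan quality. This stands as far as it goes. It does not close the gap, because the targetable-site and overlap conditions are themselves Section 3.2.3 criteria, and overlap depends on a dose distribution that exists only once a plan is made. Parts of 7.2 also use eligibility wording, as in the epidural-gap condition and the passage on the proximal bronchial tree plus 2 cm.

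A reader might infer more than the documents support:

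- *That site rules exist only in Section 7.2.* Sections 3.2.3 and 3.2.7 impose site conditions on both arms, and Appendix II also lists dose constraints.
- *That exclusion can occur only in Arm B.* Section 6.4 has imaging submitted for all registered patients, so an Arm A patient could also be found ineligible, although no review of those scans for targetability is described.
- *That one failed site leaves the patient with none.* The Section 7.2 priority list allows another site to be chosen.
- *That a target next to bowel is barred.* Section 7.2 explains how to plan such targets.
- *That the bias favors Arm B.* Section 11.0 leaves the irradiated lesion out of response assessment, so difficulty at that site need not predict response elsewhere.

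**Conclusion.** The concern holds in a limited form. An undefined entry criterion, whose practical test comes after randomization in one arm, is combined with an exclusion rule that has no time limit and no blinding. Site-related ineligibility is more likely to be found and excluded in Arm B.

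The size is conditional. With 4 of 72 dropped from Arm B only, one-sided type I error lies between 0.132 and 0.085 as the response rate of those dropped goes from 0% to 30%. With 8 of 72 it lies between 0.173 and 0.068. There is no bias if they respond like the rest. The exclusion counts and response rates are assumptions, and the documents do not determine the direction, so these figures do not show that the trial is tilted toward a positive result. They show that the error rate of the primary test would depend on something the plan could remove by wording.

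Separately, Section 7.2 is inconsistent about bone targets. The axial-skeleton definition leaves a limb-bone lesion without a location. Yet the Simulation text gives femoral metastases as an example, the spillage criteria say "Elliptically shaped metastases as well as extremity metastases may not meet these guidelines", and Group 6 of Table 5-6 covers non-spinal osseous tumors generally. This is a drafting conflict; no exclusion from the analysis is shown to follow from it.

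**What to change.** 1. In 13.6 and 12.5, state that ineligibility for the primary analysis is judged only on information available before randomization, by someone blind to arm. State also that a patient whose site proves untreatable at planning, or overlaps the measurable site, stays in the assigned arm and is followed for response. The follow-up waiver in 12.5 needs a matching exception.
2. Have the intended radiotherapy site recorded for every patient in both arms before randomization.
3. Reconcile the axial-skeleton definition in 7.2 iv with the Simulation text, the spillage criteria and Table 5-6 Group 6. This review takes no position on which sites may be treated.

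The location categories in 7.2 iv should not become new eligibility limits as a by-product; that could narrow the population.

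The cost is wording, one additional baseline item, and response follow-up of a few more patients. Unirradiated Arm B patients who stay in dilute the effect: under the assumptions above, power is about 89% with 4 such patients and 87% with 8.
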